6.1.3 Safety analyses

Safety analyses for the laboratory assessments, vital signs, ECG and physical exam data will use the study visit window rules used to assign observations to visits as defined above in [Table 1.2](#).

6.2 Handling of Dropouts, Missing Data, and Outliers

Missing data will not be imputed for safety analyses. The safety evaluations will be performed on observed data only.

For AEs with partial or missing onset or stop dates:

AE stop date will be imputed first as:

- If stop date is completely missing, assume it is ongoing (no imputation);
- For a partial AE stop date:
 - day is missing, then take the last day of the month
 - both day and month are missing, then take the last day of the last month that the patient was on study

Then AE onset date will be imputed as:

- If onset date is completely missing: the first dose date
- For a partial AE onset date:
 - day is missing:
 - Partial date < the first dose date: last day of the month
 - Partial date = the first dose date: the first dose date
 - Partial date > the first dose date: first day of the month
 - both day and month are missing ie only the year is available:
 - Partial date < the first dose date: December 31st
 - Partial date = the first dose date: the first dose date
 - Partial date > the first dose date: January 1st

If the imputed AE onset date is after the AE stop date/imputed AE stop date, then the onset date will be set to the AE stop date/imputed AE stop date.

The imputed dates will not be listed. Study day relative to the first dose of double-blind study drug associated with missing or partial dates will not be displayed in AE listings.

In the event that a partial date (month/year or year) for concomitant medication is available, this information will be used as follows:

- When both month and year are available – first day of the month will be used for start date and the last day of the month will be used for the stop date.
- When only year is available – January 1st will be used for the start date and December 31st will be used for the stop date.

The imputed dates will only be used to determine whether a concomitant medication will be classified as prior medication or concomitant medication.

For patients who complete the NPSI assessment, but have 1 incomplete answered question, the total score will be computed as 10 times sum of scores of 9 descriptors divided by 9. If more than 1 question is missing, then the total score will be missing. Missing questions will not be imputed for the subscores.

For patients who complete the BPI-DPN assessment Questions 9A-G and have less than 4 missing questions, the Interference score averaged Questions 9A-G will be computed as the mean of the answered questions. If 4 or more questions are missing, then the Interference score will be set to missing.

The Hospital Anxiety and Depression Scale (HADS) is collected only at Screening and imputation of missing data are not critical for this assessment.

No rules for outlier detection are planned.

6.2.1 Observed Cases Datasets

The mixed-effects model for repeated measurements (MMRM) will be performed based on a missing at random (MAR) assumption using data actually observed - observed cases (OC) dataset. The OC datasets will be used for analysis of the primary efficacy as well as all secondary efficacy and other efficacy endpoints. This dataset will not impute any values for missing observations, unless mentioned otherwise.

6.2.2 Pattern-mixture Model

As a sensible sensitivity analysis to the MMRM, a method for missing value imputation based on pattern-mixture model (PMM) will be used to analyze the data under the assumption that the data is missing not at random (MNAR): missingness depends on the unobserved values and cannot be predicted solely based on a patient's observed data. It is assumed that the great majority of missing data are caused by patients discontinuing prior to the study visit at which primary endpoint data are collected and the resulting missing data will have a monotone pattern. There may also be some small amount of non-monotone missing data when patients skip intermediate visits but return for evaluations at subsequent visits.

CONFIDENTIAL

Methods will be adopted to estimate for both non-monotone and monotone missing data patterns. The PMM analysis will serve as the primary sensitivity analysis of the primary efficacy endpoint (see [Section 7.6.3](#) for more details).

7. Statistical Methods

7.1 General Principles

All data processing, summarization and analyses will be performed using Hosted SAS Environment / Version 9.4 (or later) of the SAS® (SAS Institute, Cary, NC) statistical software package.

The following principles will be applied to all tables, figures, and listings (TFLs) unless otherwise stated:

Principle	Value
Significant tests	2-sided and use a 5% significance level for the main effect of study treatment
Treatment group labels and order presented	Placebo LX9211 100 mg/10 mg LX9211 200 mg/20 mg Total (if applicable)
Tables	Data in summary tables presented by study drug group, assessment (where applicable) and visit (where applicable)
Listings	All data collected presented by study drug group, center, patient, and visit (where applicable), date, unless otherwise specified
Descriptive summary statistics for continuous variables	Number of patients/observations with non-missing data (n), mean, standard deviation (SD), median, minimum and maximum. If n=0 then other statistics will be blank.
Descriptive summary statistics for categorical variables	Frequency counts and associated percentages [n (%)] presented to 1 decimal place.
Denominator for percentages	Number of patients in the analysis population, unless stated otherwise in table shell(s)
Include "Missing" as category	Yes, when the number missing is greater than 0 for at least 1 treatment group
Display for 0 percentages	Leave Blank
Display for treatment compliance and percentage change from Baseline	Present mean and median to 1 decimal place and SD to 2 decimal places
Display to 1 more decimal place than collected value	Mean Mean Difference Median Confidence Interval

Statistical Analysis Plan Final v3.0

Lexicon Pharmaceuticals, Inc.
Protocol ID: LX9211.1.201-DPN

Labcorp Study ID: 000000198624

Principle	Value
Display to 2 more decimal places than collected value	SD Standard Error
Display for p-values	x.xx for p-value > 0.05 x.xxx for p-value ≤ 0.05 and ≥ 0.001 <0.001 for p-value < 0.001
Limit of precision for displays	3 decimal places
Date Format	DDMMYY YYYY
Display for analysis not done	NC (not calculated), NA (not applicable), ND (not done), or NR (not reported). Refer to table shells.

For continuous efficacy variables that are derived as percentage change from Baseline outcomes, the applied analyses and their results will be used for descriptive purposes.

Analysis and summarization of treatment group comparisons for the safety endpoints will be reported in their original measurement units and converted values to accommodate regulatory review by the Food and Drug Administration and external authorities, where appropriate.

All significance tests will be 2-sided and use a 0.05 α -level unless specified otherwise.

7.2 Patient Disposition and Data Sets Analyzed

Patient disposition will be listed and summarized by treatment group and overall, and will include the number and percentage of patients:

- Screened
- Entered single-blind placebo Run-in Period
- Discontinued single-blind placebo Run-in Period
- Randomized
- Randomized and not treated
- Treated
- Completed double-blind Treatment Period
- Discontinued double-blind Treatment Period
- Entered optional PK substudy
- Entered optional qualitative patient interview substudy
- Completed single-blind placebo Safety Follow-up Period
- Discontinued single-blind placebo Safety Follow-up Period

CONFIDENTIAL

Document Date: 07JUN2022

Page 23 of 55
ST-AD-008 version 05

- Included in each study population (ITT, mITT, PP, PK – Substudy, PK - C_{trough} and Safety)

The number and percentage of patients who complete the study and who discontinue early (including a breakdown of the primary reasons for discontinuation), will be presented for the ITT population. In addition, the number of patients who discontinue from the double-blind Treatment Period and single-blind Safety Follow-up Period will be summarized by treatment group, respectively.

A summary of patient enrollment by site will also be provided by treatment group and overall for the ITT population. A summary of patient enrollment by randomization strata of baseline pain severity (moderate or severe pain, based on ADPS) will also be provided by treatment group, respectively.

Randomization strata will be collected in the Interactive Voice/Web Response System (IXRS) and it is defined as the average of the scores recorded in the pain diary, ie, Question 5 of the BPI-DPN, during the 2-week single-blind Run-in Period. The rounded average score will be classified as below:

- Moderate: [5-7]
- Severe: [8-9]

A summary of the reasons for screen failure as well as the number of patients screened but not randomized will be produced. No other information for screen failures will be presented.

7.3 Protocol Deviations

All-important protocol deviations leading to exclusion from the PP population (see [Section 5.3.1](#)) will be listed and summarized by study drug group for the mITT population.

The deviations will be identified before data are unblinded.

7.4 Demographics and Other Baseline Characteristics

Demographic and baseline characteristics will be listed and summarized by treatment group and overall for the mITT population. Standard descriptive statistics will be presented for the continuous variables of:

- Age at time of Informed Consent (years)
- Weight (kg), to convert pounds (lbs) to kilograms, multiply the pound value by 0.45359237
- Height (cm), to convert inches (in) to centimeters, multiply the inches value by 2.54

Statistical Analysis Plan Final v3.0

Lexicon Pharmaceuticals, Inc.
Protocol ID: LX9211.1.201-DPN

Labcorp Study ID: 000000198624

- Body mass index (BMI) (kg/m²)
- Sitting systolic blood pressure (BP) (mm Hg)
- Sitting diastolic BP (mm Hg)
- Pulse rate (beats per minute [bpm])
- Respiration rate (breaths/min)
- Temperature (C), to convert Fahrenheit (F) to Celsius, (Fahrenheit value (F) – 32) * 5/9
- HADS-Depression and HADS-Anxiety subscores

The total counts and percentages of patients will be presented for the categorical variables of:

- Age at time of Informed Consent (grouped as <75 years, ≥ 75 years)
- Sex
- Race
- Ethnicity
- Fertility status (females only)
- Method of contraception
- Baseline pain severity categorized by randomization strata (as derived using average pain scores collected during the 14-day Run in data)
- Baseline ADPS (as derived using week 2 of Run-in data)
- DPNP drug use (Yes, No)

A summary of Baseline physical examination data will be presented by treatment group and overall for the mITT population.

Other baseline measurements, such as laboratory evaluations and ECG, will be summarized by treatment group with the post-Baseline measurements.

No formal tests of statistical significance will be performed on the demographic and Baseline characteristics data.

7.4.1 Medical History

Medical history will be coded using the Medical Dictionary for Regulatory Activities (MedDRA) [Version 23 (or a later version if updated during the study)]. All medical history will be listed, and the number and percentage of patients with any medical history will be summarized for the mITT population by System Organ Class (SOC) and Preferred Term (PT) for each treatment group and overall.

CONFIDENTIAL

Document Date: 07JUN2022

Page 25 of 55
ST-AD-008 version 05

7.4.2 Prior and Concomitant Medications

Medications received prior to or concomitantly with study drug will be coded using the World Health Organization (WHO) Drug Dictionary [Version B3 Sep2020 (or a later version if updated during the study)], Anatomical Therapeutic Chemical (ATC) Classification codes.

Prior medications and concomitant medications are defined as follows:

- Prior medications are those taken prior to the first dose date of double-blind treatment, and have a stop date before first dose date of double-blind treatment.
- Concomitant medications are those with a start date on or after the first dose date of double-blind treatment, or those with a start date before the first dose date of double-blind treatment and a stop date on or after the first dose date of double-blind treatment.

If a medication cannot be classified as "prior" or "concomitant" after applying imputation rules for missing/incomplete dates, it will be classified as concomitant.

Prior medications, concomitant medications taken during double-blind Treatment Period (excluding prohibited and rescue concomitant medications), prohibited concomitant medications taken during double-blind Treatment Period, and concomitant medications started during Safety Follow-up Period (those medications starting after the last dose of double-blind study drug and through the end of the patient's Safety Follow-up Period) will be summarized separately by treatment group and overall for the mITT population.

The number and percentage of patients using each medication will be displayed together with the number and percentage of patients using at least 1 medication within each therapeutic class (ATC-Level 2), chemical subgroup (ATC-Level 4), and generic term.

The percentage of patients who need rescue medication during the double-blind Treatment Period will be summarized descriptively by treatment group and overall for the mITT population.

Prior medications, concomitant medications and rescue concomitant medications will be listed separately.

7.5 Measurements of Treatment Compliance

Percentage compliance in the double-blind Treatment Period will be calculated as:

$$(\text{number of actual tablets taken}) * 100 / \text{Number of tablets expected to be taken}$$

Where actual tablets taken will be defined as the total number of tablets dispensed minus the total number of tablets returned during the double-blind Treatment Period. The number of tablets expected to be taken will be defined as the number of days within the double-blind Treatment Period.

Percentage compliance will be summarized descriptively by treatment group and overall for the Safety population.

The number and percentage of compliant patients will be presented by treatment group and overall for the Safety population, where compliant is defined as percentage compliance between 80.0% and 100.0% inclusive. The following percentage compliance categories will also be presented:

- <80.0%
- 80.0-100.0%
- >100.0%

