7.1.2 Packaging, Labeling, and Storage

LX9211 50-mg tablets (and matching placebo) are packaged in 30 cc high density polyethylene (HDPE) bottles containing pharma coil and a child resistant polyethylene screw cap with induction seal. Each bottle contains 2 tablets.

LX9211 20-mg and 10-mg tablets (and matching placebo) are packaged in 30 cc HDPE bottles containing pharma coil and a child resistant polyethylene screw cap with induction seal. Each bottle contains 20 tablets.

LX9211 and matching placebo tablets in HDPE bottles should be stored at 25°C (77°F); excursions are permitted 15°C to 30°C (59°F to 86°F). Stability of all the strength tablets LX9211 (50-mg, 20-mg, and 10-mg) and matching placebo is ongoing.

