7.4 Administration of Study Drug

LX9211 (50 mg, 20 mg, and 10 mg) will be supplied in tablet form to be taken orally. A placebo, identical in appearance to the LX9211 tablets, will be taken by patients assigned to the placebo group.

On Day 1 of the Run-in Period, at the study facility, patients will be given 4 tablets from their bottle of Run-in study drug and will swallow it with 8 ounces (240 mL) of room temperature water. On Days 2 through 14, patients will be instructed to take their daily dose of study drug before the first meal of the day with 8 ounces of room temperature water. If a patient misses a dose by more than 12 hours, that dose should be skipped, and the next dose should be taken as scheduled. No double doses should be taken, and dose reductions are not permitted.

On Day 1 of the double-blinded Treatment Period, at the study facility, patients will be given their loading dose of study drug with 8 ounces (240 mL) of room temperature water to facilitate swallowing. Each patient's mouth will be checked to ensure they have swallowed the tablets. Patients are permitted a light meal prior to arrival at the study facility on Day 1.

On Day 2 - Week 6 Visit, except for clinic visit days, patients will be instructed to take their daily maintenance dose of study drug before the first meal of the day. Study drug should be taken with 8 ounces (240 mL) of water and should be taken whole. If a patient misses a dose by more than 12 hours, that dose should be skipped and the next dose should be taken as scheduled. No double doses should be taken, and dose reductions are not permitted. On the morning of clinic visits, patients are allowed a light meal prior to the visit.

The Study schema is presented in Figure 5.1-1. Details of study drug administration are provided in Table 7.4-1.

Treatment Group	Loading Dose (Day 1)	Daily Maintenance Dose (Day 2 Visit to Week 6 / EOT/EW)
Group 1: LX9211 100 mg/10 mg	2 x 50-mg LX9211 tablets + 2 x Placebo tablets	1 x 10-mg LX9211 tablet, qd
Group 2: LX9211 200 mg/20 mg	2 x 50-mg LX9211 tablets + 2 x 50-mg LX9211 tablets	1 x 20-mg LX9211 tablet, qd
Group 3: Placebo	2 x Placebo tablets + 2 x Placebo tablets	1 x Placebo tablet, qd

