7.4.1 Treatment Compliance

Patients will be instructed to bring their study drug bottles, including empty bottles and any unused study drug, to each clinic visit. Pill counts will be performed at each clinic visit by a member of the site staff to determine compliance. Pill count will be recorded on the study drug eCRF.

Treatment compliance percentage will be calculated as:

(Number of tablets dispensed – Number of tablets returned) X 100 Number of tablets expected to be taken

The number of tablets expected to be taken is equal to the number of days since the last visit. The Investigator/qualified designee will remind patients at each visit regarding the importance of taking 1 tablet each morning per protocol. Patients will be deemed "compliant" if their calculated compliance is between 80% and 100%, inclusive. If a patient's compliance is noted to be less than 80% or greater than 100%, the Investigator will ask the patient for the reason(s) of non-compliance with the dosing instructions, and clearly record the reason(s) in the source documents and on the eCRF.

If a patient's compliance is noted to be less than 80% or greater than 100% on 2 consecutive visits, the patient should be counseled by study personnel, and the Sponsor/designee should be contacted to determine study continuation.

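### SAP 7.5 expects one tablet per day although Day 1 is four tablets in every arm, so on its literal wording full adherence scores about 107% and is not classed as compliant

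*SAP*

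**What the plan says.** SAP 7.5 computes percentage compliance in the double-blind period as tablets taken over tablets expected. Tablets taken are "defined as the total number of tablets dispensed minus the total number of tablets returned during the double-blind Treatment Period". For the denominator it says: "The number of tablets expected to be taken will be defined as the number of days within the double-blind Treatment Period". It then classifies patients: "compliant is defined as percentage compliance between 80.0% and 100.0% inclusive", with below 80.0% and above 100.0% as the other two classes.

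Protocol 7.4.1 has the same kind of denominator for each visit interval: "The number of tablets expected to be taken is equal to the number of days since the last visit". It also treats only 80% to 100% as compliant. Sites must record a reason outside that band, and must counsel the patient and contact the sponsor if compliance is "less than 80% or greater than 100% on 2 consecutive visits".

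The dosing table in Protocol 7.4 gives four tablets on Day 1 in every group (for Group 1, "2 x 50-mg LX9211 tablets + 2 x Placebo tablets") and one tablet daily from Day 2. Run-in Day 1 is also four tablets: "patients will be given 4 tablets from their bottle of Run-in study drug".

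SAP 5.3.1 excludes patients with study drug compliance below 80% from the PP population, using exposure and drug accountability data. It does not name the SAP 7.5 formula.

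**The concern.** The numerator is in tablets and the denominator in days. The two agree only if every day is a one-tablet day, and Day 1 is not. Neither SAP 7.5 nor Protocol 7.4.1 adjusts for the three extra tablets or removes the loading dose from the count.

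Two things could follow. The compliance table could show fully adherent patients as something other than compliant. The 80% cut would also no longer mean 80% of scheduled tablets, which matters if the PP rule relies on it.

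**Working it through.** The plan states no compliance value for a fully adherent patient, so there is no figure to reproduce.

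**Inputs**
- Day 1: 4 tablets. Day 2 onward: 1 tablet per day (Protocol 7.4 dosing table).
- Diary Week 6 ends on Day 42 (SAP Table 1.1). The Week 6 Visit is targeted at Day 43 (SAP Table 1.2), with a window of ±3 days (Protocol Appendix A).
- Compliant class: 80.0% to 100.0% inclusive (SAP 7.5).

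**Formulas.** Let D be the days counted and L the last dosing day counted.
- Tablets at full adherence: 4 + (L − 1) = L + 3 with loading tablets, or L − 1 without.
- Score: 100 × tablets / D.
- Lowest passing count: 0.8 × D rounded up, which is 34 for D = 42 (33.6) and 35 for D = 43 (34.4).
- Missed home doses that still pass: tablets at full adherence minus that count.

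| D | L | Score, loading counted | Missed doses that pass | Score, loading not counted | Missed doses that pass |
|---|---|---|---|---|---|
| 42 | 42 | 45/42 = 107.1% | 45 − 34 = 11 | 41/42 = 97.6% | 41 − 34 = 7 |
| 43 | 43 | 46/43 = 107.0% | 46 − 35 = 11 | 42/43 = 97.7% | 42 − 35 = 7 |
| 42 | 43 | 46/42 = 109.5% | 46 − 34 = 12 | 42/42 = 100.0% | 42 − 34 = 8 |
| 43 | 42 | 45/43 = 104.7% | 45 − 35 = 10 | 41/43 = 95.3% | 41 − 35 = 6 |

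The first two rows use matched spans; the last two do not.

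**Visit window, matched spans, loading counted.** With 39 days the score is 42/39 = 107.7%. With 46 days it is 49/46 = 106.5%. It stays above 100% throughout.

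**Fixed denominator and an early visit.** Take a Week 6 Visit on Day 40 with no dose counted that day. Full adherence is then 39 + 3 = 42 tablets, giving 42/42 = 100.0% or 42/43 = 97.7%. This is the only route to 100% or below with loading tablets counted, and it needs a visit 2 to 3 days early.

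**What the formula rewards.** At 45/42 a patient has to miss three doses to score 100.0% (42/42). If days run only to the last dose, a patient who stops after 14 fully adherent days scores 17/14 = 121.4%.

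**Effect on the 80% cut.** With matched spans, 11 missed doses pass if loading tablets count and 7 pass if they do not. Patients missing 8 to 11 home doses are therefore classified by a convention that the SAP does not state.

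**Protocol 7.4.1.** The run-in tablets come from the patient's own bottle, so they enter the pill count: 4 + 13 = 17 tablets over 14 days is 121.4%. For the interval from Day 1 to Week 2, full adherence is 17/14 = 121.4% with loading tablets and 13/14 = 92.9% without. A fully adherent patient therefore meets the two-consecutive-visit trigger at Visits 3 and 4 only if the site counts the loading tablets.

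**The case against.** The best defence is that the loading tablets were never meant to be in the count. Protocol 7.4.1 describes a pill count on bottles that patients bring back, built around one tablet each morning. The 50-mg tablets and matching placebo are packed separately ("Each bottle contains 2 tablets") and swallowed at the site under a mouth check. Leave them out and full adherence is compliant in all four nominal cases.

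That reading is plausible, and it stands as an alternative. It does not rescue the formula: one tablet is still expected for Day 1 and none is counted, so the 80% cut becomes stricter and not correct. Nor do the documents settle the matter in its favour. The Protocol synopsis uses the word dispensed for the four run-in tablets given at the site, and SAP 7.5 counts all tablets dispensed without exception.

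A second objection also stands in part. The values 104.7% and 109.5% come from mismatched spans at a nominal Day 43 visit. They are not a general range for adherent patients, and an early visit with a fixed denominator can score 100% or less.

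Third, the consequence is small. All arms take four tablets on Day 1, so no arm is favoured. The PP analysis is supportive (SAP 7.6). Anyone in the 8-to-11 band must also meet the other PP conditions, including at least 5 weeks of treatment and an evaluable Week 6 ADPS. The documents do not show how many such patients there are. All of this is accepted.

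**Conclusion.** SAP 7.5 states a rule that does not fit the dosing schedule under either reading. This is more than a missing detail. The size rests on two assumptions, which should be kept visible: the loading tablets count as dispensed, and days and doses are counted over the same span.

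The effect is confined to the descriptive compliance table, to site queries under Protocol 7.4.1 and, if SAP 5.3.1 relies on this measure, to a modest shift in the PP cut.

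Four stronger readings are tempting and are not supported:
- *Every fully adherent patient scores above 100%.* The early-visit cases show otherwise, and so does the reading that leaves out loading tablets.
- *Adherent patients drop out of PP, or the primary result is at risk.* The PP rule has only a lower limit, and the primary analysis is on the mITT population.
- *The run-in 80% entry criterion is looser than stated.* Protocol 5.1.2 and inclusion criterion 10 cite no formula. The expected amount of run-in placebo could simply mean 17 tablets.
- *The correct cut is 9 missed doses.* That holds only if Day 1 is counted. If Day 1 is excluded, it is 8.

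**What to change.** In SAP 7.5, define expected tablets as those scheduled from Day 1 through a named last counted dosing day L, including for patients who stop early. Count tablets taken over the same days, and treat Day 1 alike above and below the line, by one of two rules:
- **A.** Expected = 4 + (L − 1), with loading tablets counted as taken. Full adherence is 45/45 (L = 42) or 46/46 (L = 43). The 80% limit is 36 of 45 or 37 of 46, and 9 missed doses pass.
- **B.** Day 1 left out of both. Full adherence is 41/41 or 42/42. The limit is 33 of 41 or 34 of 42, and 8 missed doses pass.

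Either works. A keeps the 80% as a share of all scheduled tablets. L has to be named under both: if 42 days are expected and a Day 43 tablet is also counted as taken, A gives 46/45 = 102.2% and B gives 42/41 = 102.4%. The Protocol synopsis describes dosing both to the end of Week 6 and to the Week 6 Visit, so those passages should be reconciled when L is set.

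State in SAP 5.3.1 that the below-80% rule uses this measure.

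Cost: one formula, one sentence and one cross-reference in the SAP, with small programming edits. No new data are needed and no dose changes. Protocol 7.4.1 should be reconciled with the dosing table at the next amendment, which should also say whether the run-in check uses its formula. That step needs IRB approval before implementation and cannot alter who has already been randomized.
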